| Table LMDD.2. Margin of Safety for Intravenous Administration of LY3303560 after 6 months of Dosing Based on Administered Dose and Predicted Human Exposure..... | | 31 |
| Table LMDD.3. Treatments Administered..... | | 39 |
| Table LMDD.4. Scoring of Neurological Examinations..... | | 50 |
| Table LMDD.5. Radiation Doses Associated with PET Imaging | | 52 |

List of Figures

| Figure | | Page |
|--|--|-------------|
| Figure LMDD.1. Illustration of study design..... | | 27 |

List of Appendices

| Appendix | | Page |
|-----------------|---|-------------|
| Appendix 1. | Abbreviations and Definitions | 66 |
| Appendix 2. | Clinical Laboratory Tests..... | 71 |
| Appendix 3. | Study Governance, Regulatory and Ethical Considerations | 74 |
| Appendix 4. | Blood and CSF Sampling Summary..... | 77 |
| Appendix 5. | Management of Infusion Reactions..... | 78 |
| Appendix 6. | Protocol Amendment I8G-MC-LMDD(d) Summary Multiple-Dose, Dose-Escalation Study to Assess the Safety, Tolerability, Pharmacokinetics and Pharmacodynamics of LY3303560 in Patients with Mild Cognitive Impairment due to Alzheimer's Disease or Mild to Moderate Alzheimer's Disease | 80 |

1. Protocol Synopsis

Title of Study:

Multiple-Dose, Dose-Escalation Study to Assess the Safety, Tolerability, Pharmacokinetics and Pharmacodynamics of LY3303560 in Patients with Mild Cognitive Impairment due to Alzheimer's Disease or Mild to Moderate Alzheimer's Disease

Rationale:

Lilly is developing LY3303560 for the treatment of Alzheimer's disease (AD). This study (I8G-MC-LMDD [LMDD]) will be the second clinical study of LY3303560 and will evaluate the effects of repeated every 4 week (Q4W) administrations in patients with mild cognitive impairment (MCI) due to AD or mild to moderate AD over 6 months (7 doses), with the option of extending the treatment period up to 12 months (up to 6 further doses).

The study aims to assess the safety, tolerability, pharmacokinetics (PK), and pharmacodynamics (PD) of multiple doses of LY3303560 to define an appropriate dose range for further clinical research.

Objectives/Endpoints:

| Objectives | Endpoints |
|---|---|
| Primary To assess the safety and tolerability after 16 weeks of multiple doses of LY3303560 in patients with MCI due to AD or mild to moderate AD | Safety and tolerability will be assessed by monitoring treatment-emergent adverse events (TEAEs) |
| Secondary 
To assess the PK of LY3303560 in serum following multiple intravenous (IV) doses of LY3303560 in patients with MCI due to AD or mild to moderate AD | Maximum serum concentration (C_{max}) and the area under the serum concentration time curve during the dosing interval (AUC_{τ}) |

Summary of Study Design:

This is a Phase 1b, multi-site, patient- and investigator-blind, placebo controlled, parallel-group study in patients with MCI due to AD or mild to moderate AD to assess the safety, tolerability, PK and PD of multiple IV doses of LY3303560.

Treatment Arms and Duration:

Patients will receive either LY3303560 or placebo as an IV infusion every 4 weeks (7 doses), after which they will be given the option of continuing the treatment up to 49 weeks (up to 6 further doses); the planned doses for Cohorts 1 and 2 are 70 and 210 mg, respectively.

Number of Patients:

A maximum of 24 patients will be enrolled.

In each cohort, up to 12 patients may be enrolled so that approximately 8 patients per cohort (6 LY3303560: 2 placebo) provide safety and PK data to steady state.

Statistical Analysis:

Safety: All summary statistics will be provided by cohort and visit. Patients who received placebo from both cohorts may be pooled into 1 group.

Safety parameters will be assessed including adverse events (AEs), magnetic resonance imaging (MRI), safety laboratory parameters, vital signs, and electrocardiogram (ECG) parameters. The parameters will be listed and summarised using standard descriptive statistics. Additional analysis will be performed if warranted upon review of the data.

Shift tables will be constructed for each dose group to assess the incidence of and changes in vasogenic oedema and microhaemorrhage counts pre- and post-dose based on MRI.

Suicide-related thoughts and behaviours based on the Columbia Suicide Severity Rating Scale (C-SSRS) will be listed by patient. Only time points and patients that show suicidal ideation/behaviour will be displayed (i.e., not all of the “no” responses will be displayed).

Potential QTc prolongation will be assessed using plots of PK data versus QTc values and providing frequencies by treatment for the following: the number of patients experiencing a maximum increase from baseline in QTcF interval according to the following categories - >30 ms and >60 ms; the number of patients with QTcF postdose values according to the following categories - >450 ms, >480 ms and >500 ms.

Pharmacokinetics: Pharmacokinetic parameters, including maximum drug concentration (C_{max}) and area under the concentration curve during the dosing interval (AUC_{τ}), will be calculated using standard non-compartmental methods of analysis and/or model-based approaches.

Imaging: Summary statistics of the flortaucipir F 18 standardised uptake value ratio (SUVr) will be provided by treatment (70 and 210 mg, and placebo) and visit (baseline and Visit 13 or Visit 20). Summary statistics of change from baseline and percentage change from baseline in SUVr will also be provided. Summary statistics may also be provided for SUVrs in individual and other composite brain regions if needed.

Changes in regional brain volume and functional connectivity in brain networks captured by MRI over the course of the study will be explored and summarised. Magnetic resonance imaging will be obtained every 8-12 weeks; therefore, a mixed model repeated measures (MMRM) may be conducted fitting baseline, treatment and study visit as fixed effects.

Additionally, the relationship between LY3303560 serum exposure and imaging endpoints may be explored graphically or by a modeling approach.

2. Schedule of Activities

2.1. Screening (Visit 1)

Study Schedule Protocol I8G-MC-LMDD (Screening Period)

| | | Comments |
|--|-----|--|
| Visit | V1 | Screening tests may occur up to 90 days before study drug administration. Tests may be conducted over approximately 3-5 screening visit days. |
| Day Relative to First Dose | -90 | |
| Study Entry and Administrative Procedures | | |
| Informed consent (before procedures/tests) | X | |
| Patient number assigned | X | |
| Demographics, height, weight, and habits | X | |
| Inclusion/exclusion review | X | |
| Previous/concomitant medications | X | |
| Preexisting conditions/AEs | X | |
| Cognitive Assessments | | |
| MMSE | X | Cognitive assessments need not be done on the same visit day, but should be completed in the following order if done on the same day: |
| FCSRT-IR | X | |
| CDR | X | |
| dCDT | X | 1) MMSE, 2) FCSRT-IR, 3) CDR, and 4) dCDT |
| Safety Assessments | | |
| Physical/neurological exam | X | |
| Single 12-lead digital ECG | X | |
| Vital signs | X | Supine blood pressure and pulse rate |
| C-SSRS (child)/SHSF | X | If the investigator determines that suicide-related behaviours have occurred, the Lilly SHSF and SHFU forms will be used to collect additional information to allow for a more complete assessment of these behaviours |
| Laboratory Assessments (local laboratory) | | |
| Coagulation tests | X | |
| Clinical laboratory tests | X | See Appendix 2 , Clinical Laboratory Tests, for details. |
| Imaging | | |
| Lumbar x-ray | X | A lumbar x-ray may be performed to rule out potential contraindications to an LP. If an x-ray was performed within 12 months of screening, it may be used. |
| MRI | X | |
| Amyloid scan (if not previously performed) | X | Any previously taken positive amyloid scan must be reviewed by central reader to confirm amyloid status. Amyloid PET tracers may include, but are not limited to, florbetapir, florbetaben, flutemetamol. |

Abbreviations: AE = adverse event; CDR = Clinical Dementia Rating; C-SSRS = Columbia-Suicide Severity Rating Scale; dCDT = digital clock drawing test; ECG = electrocardiogram; FCSRT-IR = Free and Cued Selective Reminding Test with Immediate Recall; MMSE = Mini-Mental State Examination; MRI = magnetic resonance imaging; PET = positron emission tomography; SHSF = Self-Harm Supplement Form; SHFU = Self-Harm Follow-Up.

2.2. MAD Treatment Period (Visits 2 to 19)

Study Schedule Protocol I8G-MC-LMDD

MAD Treatment Period (Visits 2 through 19)

| Visit | V2 ^a Rand | V3 | V4 | V5 | V6 | V7 | V8 | V9 | V10 | V11 | V12 | V13 | V14 | V15 | V16 | V17 | V18 | V19 |
|--|-------------------------|----------------|------|----|----|----|-----------------|-----------------|-----------------|------------------|------------------|------------------|------------------|------------------|------------------|------------------|------------------|------------------|
| Day Relative to First Dose | -8 | 1 ^b | 2 | 4 | 8 | 15 | 29 ^b | 57 ^b | 85 ^b | 113 ^b | 141 ^b | 169 ^b | 197 ^b | 225 ^b | 253 ^b | 281 ^b | 309 ^b | 337 ^b |
| Week | | 1 | 1 | 1 | 2 | 3 | 5 | 9 | 13 | 17 | 21 | 25 | 29 | 33 | 37 | 41 | 45 | 49 |
| Tolerance Interval for Visit (days) | ±7 ^a | 0 | +4 h | ±1 | ±1 | ±1 | ±4 | ±4 | ±7 | ±7 | ±7 | ±7 | ±7 | ±7 | ±7 | ±7 | ±7 | ±7 |
| Dosing | | | | | | | | | | | | | | | | | | |
| Study medication administered | | D1 | | | | | D2 | D3 | D4 | D5 | D6 | D7 | D8 | D9 | D10 | D11 | D12 | D13 |
| Administrative Procedures | | | | | | | | | | | | | | | | | | |
| Body weight | X | | | | | | | | | | | 0 | | | | | | 0 |
| Previous/concomitant medications | X | X | X | X | X | X | X | X | X | X | X | X | X | X | X | X | X | X |
| Inclusion/exclusion review | X | | | | | | | | | | | | | | | | | |
| Preexisting conditions/AEs | | X | X | X | X | X | X | X | X | X | X | X | X | X | X | X | X | X |
| Cognitive Assessments and Functional Scales^{c,d} | | | | | | | | | | | | | | | | | | |
| ADAS-Cog ₁₄ | X | | | | | | | | | | | | X | | | | | |
| ADCS-MCI-ADL24 | X | | | | | | | | | | | | X | | | | | |
| MMSE | X | | | | | | | | | | | | X | | | | | |
| NTB | X | | | | | | | | | | | | X | | | | | |
| dCDT | X | | | | | | X | X | X | X | X | X | X | X | X | X | X | |
| Safety Assessments | | | | | | | | | | | | | | | | | | |
| Vital signs | X | 0, 0.5, 2 | 24 | 72 | X | X | 0, 0.5, 2 | 0, 0.5, 2 | 0, 0.5, 2 | 0, 0.5, 2 | 0, 0.5, 2 | 0, 0.5, 2 | 0, 0.5, 2 | 0, 0.5, 2 | 0, 0.5, 2 | 0, 0.5, 2 | 0, 0.5, 2 | |
| C-SSRS/SHSF | X | 0 | X | X | X | X | 0 | 0 | 0 | 0 | 0 | 0 | 0 | 0 | 0 | 0 | 0 | 0 |
| Physical examination | | 0 | | | X | | | 0 | 0 | 0 | 0 | 0 | 0 | 0 | 0 | 0 | 0 | 0 |
| Neurological examination | | 0 | 24 | | X | X | 0 | 0 | 0 | 0 | 0 | 0 | 0 | 0 | 0 | 0 | 0 | 0 |
| Triple 12-lead digital ECG | X | 0, 0.5, 2 | 24 | 72 | X | X | 0, 0.5, 2 | 0, 0.5, 2 | 0, 0.5, 2 | 0, 0.5, 2 | 0, 0.5, 2 | 0, 0.5, 2 | 0, 0.5, 2 | 0, 0.5, 2 | 0, 0.5, 2 | 0, 0.5, 2 | 0, 0.5, 2 | |

continued

Study Schedule Protocol I8G-MC-LMDD

MAD Treatment Period (Visits 2 through 19) (concluded)

| Visit | V2 ^a Rand | V3 | V4 | V5 | V6 | V7 | V8 | V9 | V10 | V11 | V12 | V13 | V14 | V15 | V16 | V17 | V18 | V19 |
|-------------------------------------|-------------------------|----------------|------|----|----|----|-----------------|-----------------|-----------------|------------------|------------------|------------------|------------------|------------------|------------------|------------------|------------------|------------------|
| Day Relative to First Dose | -8 | 1 ^b | 2 | 4 | 8 | 15 | 29 ^b | 57 ^b | 85 ^b | 113 ^b | 141 ^b | 169 ^b | 197 ^b | 225 ^b | 253 ^b | 281 ^b | 309 ^b | 337 ^b |
| Week | | 1 | 1 | 1 | 2 | 3 | 5 | 9 | 13 | 17 | 21 | 25 | 29 | 33 | 37 | 41 | 45 | 49 |
| Tolerance Interval for Visit (days) | ±7 ^a | 0 | +4 h | ±1 | ±1 | ±1 | ±4 | ±4 | ±7 | ±7 | ±7 | ±7 | ±7 | ±7 | ±7 | ±7 | ±7 | ±7 |

Dosing

| | | | | | | | | | | | | | | | | | | |
|-------------------------------|--|----|--|--|--|--|----|----|----|----|----|----|----|----|-----|-----|-----|-----|
| Study medication administered | | D1 | | | | | D2 | D3 | D4 | D5 | D6 | D7 | D8 | D9 | D10 | D11 | D12 | D13 |
|-------------------------------|--|----|--|--|--|--|----|----|----|----|----|----|----|----|-----|-----|-----|-----|

Imaging

| | | | | | | | | | | | | | | | | | | |
|--------------------------------------|----------------|--|--|--|--|--|---|--|---|--|--|----------------|--|--|---|--|--|----------------|
| MRI ^f | | | | | | | X | | X | | | X | | | X | | | X |
| Flortaucipir F 18 PET ^{d,h} | X ^g | | | | | | | | | | | X ^h | | | | | | X ^h |

Laboratory Assessments (central laboratory unless otherwise noted)

| | | | | | | | | | | | | | | | | | | |
|--|---------------------|--------------------|----|--|---|---|--------------------|--------------------|---|---|---|--------------------|---|---|---|---|--------------------|----------------|
| Lumbar puncture ^{d,j} | X ⁱ | | | | | | | | | | | X ^l | | | | | | X ^l |
| Blood RNA | X | | | | | | X | | | | | | | | | | | X |
| Pharmacogenetic sample | X | | | | | | | | | | | | | | | | | |
| Clinical laboratory tests | X (local lab) | 0 | X | | X | | X | X | X | X | X | X | X | X | X | X | X | |
| Coagulation tests (local laboratory) ^{j,k} | X | | | | | | | | | | | X | | | | | | X |
| Serum LY3303560 PK (hours) ^e | | 0.5, 2, 4, 8 | 24 | | X | X | 0, 0.5, 2, 4, 8 | 0, 0.5, 2, 4, 8 | 0 | | 0 | 0, 0.5, 2, 4, 8 | | | 0 | | 0, 0.5, 2, 4, 8 | |
| Serum for immunogenicity | X | | | | X | X | 0 | | X | | | 0 | | | 0 | | 0 | |
| Plasma Tau PD (hours) ^e | | 0, 0.5, 2, 4, 8 | 24 | | X | X | 0, 0.5, 2, 4, 8 | 0, 0.5, 2, 4, 8 | 0 | | 0 | 0, 0.5, 2, 4, 8 | | | 0 | | 0, 0.5, 2, 4, 8 | |
| Stored EDTA plasma and serum | | 0 | 24 | | X | | 0 | 0 | 0 | 0 | 0 | 0 | | | 0 | | 0 | |
| Stored serum for possible exploratory immune safety laboratory tests | X | | | | | | | | X | | | X | | | X | | | |

Abbreviations: ADAS-Cog14 = 14-item Alzheimer's Disease Assessment Scale – Cognition; ADCS-MCI-ADL24 = 24-question Alzheimer's Disease Cooperative Study/Activities of Daily Living scale adapted for MCI patients; AE = adverse event; CDR = Clinical Dementia Rating; CRF = case report form; CSF = cerebrospinal fluid; C-SSRS = Columbia-Suicide Severity Rating Scale; D = dose; dCDT = digital clock drawing test; ECG = electrocardiogram; ED = early discontinuation; EDTA = ethylene diamine tetraacetic acid; FU = follow-up; IV = intravenous; LP = lumbar puncture; MMSE = Mini-Mental State Examination; MRI = magnetic resonance imaging; NTB = Neuropsychological Test Battery; PD = pharmacodynamics; PET = positron emission tomography; PK = pharmacokinetics; rand = randomisation; RNA = ribonucleic acid; SC = subcutaneous; SHSF = Self-Harm Supplement Form.

Note:

- (i) PK time points indicated as zero (0) denote trough samples immediately prior to study drug infusions/injections. Other assessments denoted as “0” will be collected prior to study drug infusions/injections. Samples listed as non-zero numbers refer to hours after the start of the IV infusion.
- (ii) The timings of safety, PK, and PD sampling are given as targets to be achieved within reasonable limits. Modifications may be made to the time points based upon the safety and PK information obtained. The scheduled time points may be subject to minor alterations; however, the actual time must be correctly recorded in the CRF. Failure to obtain samples due to clinical issues, such as problems with venous access, will not be considered a protocol violation.
- (iii) Order of assessments should be as follows: ECGs, vital signs (after appropriate rest), PK (when applicable).
 - a Tests may be conducted over approximately 3-5 visit days.
 - b Patients may be admitted on Day -1, to perform pre-dose tests, at the discretion of the site. For the first 6 infusions, patients must be observed closely for at least 4 hours following each infusion of LY3303560. After the first 6 infusions, a minimum post-infusion observation time of 2 hours will be required for all subsequent infusions. If any patient shows symptoms of an infusion reaction, the observation time will be increased to a minimum of 8 hours for that infusion and all future infusions. If deemed necessary, for safety or feasibility reasons, patients may remain in the investigative site for a longer duration at the discretion of the investigator.
 - c Assessments need not be done on the same visit day but should be completed in the following order if done on the same day (with approximately 4 hours separating NTB and ADAS-Cog₁₄ to avoid testing fatigue): 1) ADAS-Cog₁₄, 2) ADCS-MCI-ADL24, 3) MMSE, 4) NTB, and 5) dCDT. All cognitive and functional assessments must be performed before LP if on the same day; therefore, some of this testing may need to be performed on a separate day.
 - d When the flortaucipir F 18 PET scan and LP have been scheduled on the same visit, the PET scan should be performed at least 24 hours after the LP. Cognitive assessments must be performed before LP if done on the same day.
 - e Pharmacokinetic sample time points are relative to the beginning of the IV infusion. The 0.5 h PK sample should be collected immediately after the 0.5 h IV infusion is completed as close as possible to the end of the infusion), followed by ECGs and vital signs 5 to 10 minutes later. On the day of dosing, postdose samples should be collected from the opposite arm to that used to administer study drug for IV infusion.
 - f If a patient discontinues before the MRI, the patient will be requested to return for this procedure even though all other study evaluations may be forgone. The MRI must be performed before a LP if conducted on same day.
 - g The V2 flortaucipir F 18 PET scan must be performed, and notification of adequate technical scan quality received from the PET imaging core laboratory, before dosing. The scan is performed after the patient qualifies based on the results of the amyloid PET scan and other screening tests. It may be performed up to 28 days prior to dosing once all screening assessments have been completed.

- h The flortaucipir F 18 PET scan should be conducted at Visit 13 should the patient follow the 25-week treatment regimen or at Visit 19 for the 49-week treatment regimen. The flortaucipir F 18 PET scan should be completed at Visit 20 if the patient discontinues treatment after Visit 13 and before Visit 19. Patients permanently discontinued from study treatment due to initiation of a prohibited medication known to prolong the QT-interval should not have an ED flortaucipir F 18 scan unless the scan can be performed prior to initiation of the prohibited medication. Patients who have continued on study after introduction of a drug known to prolong QT interval (with sponsor approval) need a minimum of 14 days or 5 half-lives, whichever is longer, without that drug prior to the flortaucipir scan.
- i The baseline V2 LP will be performed no closer than 24 hours before first dose. Dosing may not proceed until patient has been at least 12 hours free of symptoms of post-LP headache, if present. Refer to Section 9.5.1 for details of sampling.
- j Coagulation test results should be reviewed before each LP. Concomitant medications should be reviewed to ensure that no changes to anticoagulation or antiplatelet therapy have occurred since the last coagulation test.
- k LPs are scheduled at either Visits 13, 19, 20, or early discontinuation. The corresponding coagulation test is required up to 2 weeks prior to the next scheduled LP.
- l The LP should be conducted at Visit 13 should the patient follow the 25-week treatment regimen or at Visit 19 for the 49-week treatment regimen. The LP should be completed at Visit 20 if the patient discontinues treatment after Visit 13 and before Visit 19.

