2.3. Follow-up Assessments (Visits 20 to 24)

Study Schedule Protocol I8G-MC-LMDD - MAD Treatment Period; Follow-up Assessments (Visits 20 to 24)

| Visit | V20 | V21 | V22 | V23 | V24 | ED |
|---|------------------------------|-----|-----|-----|-----|----|
| Day Relative to First Dose (for 25-week treatment phase) ^a | 189 | 203 | 231 | 259 | 287 | |
| Week (for 25-week treatment) ^a | 27 | 29 | 33 | 37 | 41 | |
| Day Relative to First Dose (for 49-week treatment phase) ^a | 351 | 365 | 393 | 421 | 449 | |
| Week (for 49-week treatment) ^a | 51 | 53 | 57 | 61 | 65 | |
| Tolerance Interval for Visit (days) | ±7 | ±7 | ±7 | ±7 | ±7 | |
| Administrative Procedures | | | | | | |
| Body weight | | | | | X | X |
| Previous/concomitant medications | X | X | X | X | X | X |
| Inclusion/exclusion review | | | | | | |
| Preexisting conditions/AEs | X | X | X | X | X | X |
| Cognitive Assessments and Functional Scales^{b,c} | | | | | | |
| ADAS-Cog ₁₄ | X | | | | | |
| ADCS-MCI-ADL24 | X | | | | | |
| MMSE | X | | | | | |
| NTB | X | | | | | |
| dCDT | X | | | | X | X |
| Safety Assessments | | | | | | |
| Vital signs | | X | X | X | X | X |
| C-SSRS/SHSF | X | X | X | X | X | X |
| Physical examination | | X | X | X | X | X |
| Neurological examination | | X | X | X | X | X |
| Triple lead digital ECG | | X | X | X | X | X |
| Imaging | | | | | | |
| MRI | | | | X | | X |
| Flortaucipir F 18 PET ^{c,d} | X (if not done at V13 or 19) | | | | | X |
| Laboratory Assessments (central laboratory unless otherwise noted) | | | | | | |
| Lumbar puncture ^{c,e,g} | X (if not done at V13 or 19) | | | | | X |
| Blood RNA | | | | | | X |
| Pharmacogenetic sample | | | | | | |
| Clinical laboratory tests | | X | X | X | X | X |
| Coagulation tests (local laboratory) ^e | X (if not done at V13 or 19) | | | | | X |
| Serum LY3303560 PK (hours) ^f | X | X | X | X | X | X |
| Serum for immunogenicity | | | | | X | X |
| Plasma Tau PD (hours) ^f | X | X | X | X | | X |
| Stored EDTA plasma and serum | | | | | | X |
| Stored serum for possible exploratory immune safety laboratory tests | | | | | | X |

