#### **5.4.5. QTcF**

The number of patients experiencing a maximum increase from baseline in QTcF interval will be summarised for each treatment according to the following categories: >30 ms and >60 ms. In addition, the number of patients with QTcF postdose values, according to the following categories: >450 ms, >480 ms and >500 ms, will be summarised by treatment.

Analyses of QTc using QTcF from ECG monitoring will be performed to judge the extent and/or risk of QT prolongation. An assessment of potential QTc prolongation will be performed using plots of PK data versus QTc values. Scatter plots will be created of QTcF versus LY3303560 concentration and change from baseline QTcF versus LY3303560 concentration (for timepoints where there is matched LY3303560 concentration and QTcF available). Placebo data will be included in the plot with concentration imputed to zero. The reference line of 450, 480, and 500 ms will be used for the QTcF versus concentration plot; while 10, 30 and 60 ms for QTcF change from baseline versus concentration plot. Analysis will be performed to assess the mean change in QTcF as a function of plasma drug concentration. The average of the triplicate QTcF measurements will be computed at each of the scheduled time points, and baseline will be the mean of the triplicate measurements collected prior to dosing at time 0 in each treatment period.

A mixed-effect model may be fitted to the QTcF change from baseline, with log –transformed plasma-drug concentration and dose included as fixed effects. The model will be run for the following ECG/PK time matched visits and time points in separate models; Visit 3(Day 1), Visit 8 (Day 27), Visit 9 (Day 57), Visit 13 (Day 169), Visit 19 (Day 337).

The following SAS code may be utilized:

```
proc mixed data=dose_sim;
by visit;
class patient;
model qtcrsult = pkresult / outp=resdat s cl alpha=0.1;
random patient;
ods output solutionf=sol;
run;
```

A second model may be run following the same model but combining all the visits together. Other time matched measures from non PK/ECG intensive days may also be considered for inclusion.

Further exploratory analyses may be conducted if required.

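### Dose 13 is given at Visit 19, where no ECG, PK, vital signs or clinical laboratory tests are scheduled, yet SAP 5.4.5 lists Visit 19 for a time-matched QTcF model and omits Visit 18

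*Protocol*

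**What the plan says.** **Dosing.** The dosing row of Protocol 2.2 ends with "D7 | D8 | D9 | D10 | D11 | D12 | D13", which places dose 13 in the Visit 19 column, Day 337.

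**Safety rows.** Vital signs and triple ECG each print "0, 0.5, 2 | 0, 0.5, 2 | 0, 0.5, 2" for Visits 16 to 18 and nothing for Visit 19. The clinical laboratory row also stops at Visit 18.

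**Sampling rows.** From Visit 13 to Visit 18 the serum PK row reads "0, 0.5, 2, 4, 8 | | | 0 | | 0, 0.5, 2, 4, 8", and its Visit 19 cell is empty. The last full profile is therefore at Visit 18, Day 309. Plasma tau and immunogenicity also end at Visit 18.

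**What Visit 19 does carry.** Adverse events, concomitant medication, weight, predose C-SSRS, physical and neurological examinations, MRI, flortaucipir PET, lumbar puncture, blood RNA and coagulation tests. Footnote b requires at least 2 hours of observation after the infusion.

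**Follow-up.** In Protocol 2.3 the vital-signs row is "Vital signs | | X | X | X | X | X": Visit 20 is blank and Visit 21 is filled. ECG and clinical laboratory tests follow the same pattern. A PK sample is scheduled at Visit 20.

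**SAP 5.4.5.** The text is permissive: "A mixed-effect model may be fitted to the QTcF change from baseline". The by-visit runs are listed for Visit 3 (Day 1), then "Visit 8 (Day 27), Visit 9 (Day 57), Visit 13 (Day 169), Visit 19 (Day 337"). Visit 18 is not in the list.

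**The concern.** The SAP describes its listed visits as ones where ECG and PK are matched in time. Visit 19 does not meet that description in the current schedule, and Visit 18, which does, is left out. A programmer who follows the SAP gets an empty run for the latest visit and no by-visit estimate from the last scheduled profile.

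The same blank cells raise a data question. As printed, dose 13 is the only one of the 13 infusions with no scheduled vital signs, ECG or clinical laboratory tests, in a study whose primary objective is safety. The serum-to-CSF analysis in Protocol 10.3.2.1 and SAP 5.5 is affected too. The on-treatment lumbar puncture at Visit 13, and the one at Visit 20 where it is done, have a serum sample at the same visit. The one at Visit 19 does not.

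**Working it through.** No power or sample-size formula applies. The check is a cell count of the schedule and a match of nominal times.

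**1. Reproduce the plan's own totals.** Protocol 2.2 has 18 visit columns (Visits 2 to 19). Appendix 4 allows 35 (+5) serum PK samples. Scheduled samples on treatment, by visit:

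V3 4 + V4 1 + V6 1 + V7 1 + V8 5 + V9 5 + V10 1 + V12 1 + V13 5 + V16 1 + V18 5 = 30.

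Adding one each at Visits 20 to 24 gives 30 + 5 = 35, which agrees. A further five-sample profile at Visit 19 would give 40. Plasma tau (31 + 4 = 35) and immunogenicity (8 + 1 = 9) also agree. None of these three totals counts the early-discontinuation sample.

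The laboratory total of 20 is ambiguous. It is 15 + 4 + 1 with Visit 19 blank and early discontinuation counted, and 16 + 4 with Visit 19 filled and early discontinuation not counted. It is not used as evidence here.

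**2. Could the table have slipped a column?** Dosing visits are Visit 3 plus Visits 8 to 19, so 1 + 12 = 13, matching doses 1 to 13. The vital-signs and ECG rows have no interior gaps, and their 24 h and 72 h entries fall under Day 2 and Day 4, which fixes the columns. From Visit 8 on, each row holds 11 entries for 12 dosing visits. The laboratory row likewise has 11 marks for those 12 visits. Moving cells cannot fill Visit 19 without emptying another dosing visit.

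**3. Match ECG and PK times on the visits in question.**

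| Visit | Day | ECG (h) | PK (h) | Pairs per patient | In SAP list |
|---|---|---|---|---|---|
| 3 | 1 | 0, 0.5, 2 | 0.5, 2, 4, 8 | 2 | yes |
| 8 | 29 | 0, 0.5, 2 | 0, 0.5, 2, 4, 8 | 3 | yes, as Day 27 |
| 9 | 57 | 0, 0.5, 2 | 0, 0.5, 2, 4, 8 | 3 | yes |
| 13 | 169 | 0, 0.5, 2 | 0, 0.5, 2, 4, 8 | 3 | yes |
| 18 | 309 | 0, 0.5, 2 | 0, 0.5, 2, 4, 8 | 3 | **no** |
| 19 | 337 | none | none | **0** | **yes** |

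If the last PK profile really belonged to Visit 19, the ECG cell there would still be blank and the Visit 19 run would still have no pairs.

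**4. Intervals for a patient who completes 49 weeks.**
- Dose 13 to the next scheduled vital signs, ECG and clinical laboratory tests (Visit 21): 365 − 337 = 28 days.
- Visit 19 lumbar puncture to the next PK sample (Visit 20): 351 − 337 = 14 days.
- Last earlier PK sample (Visit 18) to the Visit 19 lumbar puncture: 337 − 309 = 28 days.

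**5. How many patients.** The documents do not say how many take the 49-week option. Assume the planned two cohorts of 6 active and 2 placebo, with placebo samples not assayed (Protocol 9.5.2). The Visit 18 pairs with a measured concentration then number between 0 (nobody continues) and 12 × 3 = 36 (all active patients continue).

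**The case against.** The other side has several good points.

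- **Monitoring.** A reader might infer that dose 13 is unmonitored. The documents do not support that: Visit 19 keeps the assessments listed above and the 2-hour observation. Protocol 9.4.2, 9.4.3 and 9.5 also allow extra vital signs, ECGs and up to 5 extra PK samples. This stands, and the point is limited to scheduled assessments.
- **Use of Visit 18 data.** A reader might also infer that Visit 18 is discarded. It is not. Its pairs enter the concentration scatter plots and can enter the optional combined-visit model, and its QTcF values enter the category counts. Only the by-visit runs omit it. This stands.
- **Weight of the model.** The model is optional, no formal hypothesis tests are planned, and an empty visit gives no output, not a wrong estimate. The primary objective concerns 16 weeks, and Protocol 5.4 sets the minimum data at Day 113. This stands and lowers the stakes.
- **CSF pairing.** The serum-to-CSF analysis is optional and could use model-based exposure. This stands in part: a model can predict the concentration at Visit 19, but no observed value is scheduled there.
- **Extraction.** The PET and lumbar-puncture rows appear one column later in Appendix 6 than in Section 2.2, although the footnotes in both places say Visit 13. Cells can therefore shift in the text as read. That is a fair caution about positions, but a shift cannot supply a twelfth entry to a row that holds eleven.

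The general permission to modify time points does not correct the SAP's list of visits.

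**Conclusion.** The plan is wrong as written on two linked points. SAP 5.4.5 names Visit 19 for a time-matched QTcF run with 0 scheduled pairs and omits Visit 18, which has 3 per patient. The schedule also gives an infusion at Visit 19 while leaving six assessment rows blank there: vital signs, triple ECG, clinical laboratory tests, serum PK, plasma tau and immunogenicity.

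The effect is confined to patients who reach Visit 19 on the 49-week option. Those who stop at 25 weeks have vital signs, ECG, clinical laboratory tests and PK all scheduled at their last dose (Visit 13). The primary 16-week objective is not touched.

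The conclusion assumes that the schedule as read shows the entries as printed. Appendix 4 supports the PK, plasma tau and immunogenicity counts, but these totals alone cannot tell Visit 18 from Visit 19. It says nothing about vital signs or ECG, and its laboratory total should not be cited as proof that Visit 19 is blank. Whether the blank cells are intended cannot be settled from the documents.

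The Visit 8 label is a minor slip. Day 27 lies inside the protocol's window of 29 ± 4 days (Days 25 to 33), so no data are misassigned.

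**What to change.** 1. Reconcile the Visit 19 column of Protocol 2.2 with its dosing row and with SAP 5.4.5. State whether the blank cells are intended. This point does not say what the schedule should contain.
2. In SAP 5.4.5, define the by-visit QTcF runs as the dosing visits where the reconciled schedule places both ECG and PK samples. As now printed, that means replacing Visit 19 (Day 337) with Visit 18 (Day 309).
3. State in the SAP which serum value will accompany the Visit 19 CSF sample in the optional exposure analysis: an observed sample if the reconciled schedule has one, or a model-based prediction.
4. Correct Visit 8 from Day 27 to Day 29.

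The cost is a short correction to the SAP visit list and a schedule clarification. SAP 5.1 already says that changes to the planned analysis need no protocol amendment and will be described in the study report. Patients attend Visit 19 in any case.
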